Abbreviations: ACQ-5 = Asthma Control Questionnaire 5-item version; AD = atopic dermatitis; BSA = body surface area; CDLQI = Children’s Dermatology Life Quality Index; DLQI = Dermatology Life Quality Index; EASI = Eczema Area and Severity Index; EQ-5D = standardized instrument developed by the EuroQol Group; EMA = European Medicines Agency; FDA = Food and Drug Administration; IGA = Investigator Global Assessment; POEM = Patient Oriented Eczema Measure; PROMIS = Patient-Reported Outcomes Measurement Information System; SCORAD = SCORing Atopic Dermatitis; SQAAQ= subcutaneous administration assessment questionnaire.

For Food and Drug Administration (FDA), primary and major secondary endpoints for Induction Period will be adjusted for multiplicity. For European Medicines Agency (EMA), primary and major secondary endpoints for Induction Period and major secondary endpoints for Maintenance Period will be adjusted for multiplicity separately (i.e. induction and maintenance endpoints will be tested separately). Details can be found in Section 6.6.

5. Study Design

5.1. Summary of Study Design

Study J2T-DM-KGAB (KGAB) [aka DRM06-AD04] is a randomized, double-blind, placebo-controlled, parallel-group study in adult and adolescent (≥ 12 to < 18 years weighing ≥ 40 kg) patients with moderate-to-severe atopic dermatitis (AD). Approximately 400 patients will be enrolled into the study. The study is comprised of 2 treatment periods (16-week Induction and 36-week Maintenance). Patients completing this 52-week study will be offered continued treatment in a separate long-term extension study J2T-DM-KGAA (DRM06-AD07). Patients who early terminate or choose not to enter the long-term extension study will undergo a follow-up visit approximately 12 weeks after the last study drug injection for safety follow-up.

5.1.1. Screening Period

Screening Period: Patients will be evaluated for study eligibility before the baseline visit (Day 1). Electronic diary collection will begin at screening.

5.1.2. Baseline and Double-Blinded Induction Period (Week 0 to Week 16)

At baseline visit (Day 1), patients who meet the study eligibility criteria will be 2:1 randomly assigned to their induction treatments with stratification based on geographic region (US versus EU versus rest of world), age (adolescent patients 12 to < 18 versus adults ≥ 18 years) and disease severity (IGA 3 versus 4). The treatment groups in the Blinded Induction Period are:

- Lebrikizumab 250 mg every 2 weeks (Q2W): 500 mg lebrikizumab administered at Baseline and Week 2 (loading dose; 2 pre-filled syringes with a pre-assembled needle safety device [PFS-NSD]) and 250 mg Q2W through Week 14.
- Placebo: 4 mL (2 PFS-NSD) administered at Baseline and Week 2 and 2 mL Q2W through Week 14.

5.1.3. Maintenance Period (Week 16 to Week 52 [36 Weeks])

5.1.3.1. Maintenance Blinded Period

After completion of the Week 16 visit, patients who have responded to treatment (defined as having an IGA of 0 or 1 or a 75% reduction in EASI from Baseline to Week 16 [EASI-75] according to IWRS system) will enter the Maintenance Period and will be re-randomized 2:2:1 to one of the following treatment groups: lebrikizumab 250 mg Q2W, lebrikizumab 250 mg Q4W, or placebo Q2W. Throughout the maintenance blinded period, patients will receive placebo, as appropriate, to maintain the study blind across treatment groups.

5.1.3.2. Maintenance Escape Period

[figure not shown]
Patients who do not achieve an IGA of 0 or 1 or an EASI-75 at Week 16, patients received topical or systemic rescue therapy between baseline to Week 16 and those patients not maintaining an EASI-50 response following re-randomization at Week 24, 32, 40, or 48 will be

assigned to an Escape Arm and receive lebrikizumab 250 mg as open-label treatment Q2W through Week 52. Patients not achieving an EASI-50 response in the Escape Arm after 8 weeks of treatment will be terminated from the study.

5.1.4. Safety Follow-up Visit

Patients who terminate early from the study or do not enroll in the long-term extension study, J2T-DM-KGAA (DRM06-AD07), will undergo a follow up visit approximately 12 weeks after the last study drug injection.

Figure KGAB.5.1 illustrates the study design.

* Responder is defined as having an IGA of 0 or 1 or a 75% reduction in EASI from Baseline to Week 16 (EASI-75)

Figure KGAB.5.1. Illustration of study design for Clinical Protocol KGAB.

5.2. Determination of Sample Size

For FDA: In the DRM06-AD01 Phase 2b study (J2T-DM-KGAF), the proportion of patients who achieved an IGA score of 0 or 1 at Week 16 using the rescue medication non-response sensitivity analysis was approximately 34.7% for lebrikizumab 250 mg Q2W versus 7.7% for placebo. A sample size of 96 for lebrikizumab 250 mg Q2W versus 48 for placebo will have more than 95% power to detect a statistically significant difference based on a two group continuity corrected chi-square test with a two-sided significance level of 0.05. However, to ensure sufficient safety information is collected and to ensure sufficient responders for the Maintenance Period, the sample size will be increased to approximately 400 in total with a randomization ratio of 2:1 lebrikizumab:placebo.

For European Medicines Agency (EMA): In the DRM06-AD01 Phase 2b study (J2T-DM-KGAF), the proportion of patients who achieved an IGA score of 0 or 1 at Week 16 using the rescue medication non-response sensitivity analysis was approximately 34.7% for lebrikizumab 250 mg Q2W versus 7.7% for placebo, and the proportion of patients who achieved an EASI-75 at Week 16 using the rescue medication non-response sensitivity analysis was approximately

48.0% for lebrikizumab 250 mg Q2W versus 11.5% for placebo. A sample size of 96 for lebrikizumab 250 mg Q2W versus 48 for placebo will have more than 95% power to detect a statistically significant difference based on a two group continuity corrected chi-square test with a two-sided significance level of 0.05 for each of the co-primary endpoints, which imply and overall power of at least 90%. However, to ensure sufficient safety information is collected and to ensure sufficient responders for the Maintenance Period, the sample size will be increased to 400 in total with a randomization ratio of 2:1 lebrikizumab:placebo.

5.3. Method of Assignment to Treatment

All patients will be randomly allocated to receive the study treatment using an electronic data capture (EDC) system at the Baseline visit. The allocation to treatment will be prospectively stratified by geographic region (US versus EU versus rest of world), age (adolescent patients 12 to <18 years versus adults \geq 18 years) and disease severity (IGA 3 versus 4). At the Baseline visit (Day 1), once a patient is considered eligible to participate in the study, demographic and stratification information will be entered into the EDC system to receive a medication number assigning a kit to a patient.

During the Maintenance Period, the EDC will be used to re-randomize a patient to a maintenance treatment based on the IGA or EASI score at Week 16 and rescue therapy usage during induction period.

6. A Priori Statistical Methods

6.1. General Considerations

Statistical analysis of this study will be the responsibility of Eli Lilly and Company (Lilly). The latest version of the Medical Dictionary for Regulatory Activities (MedDRA) will be used.

Analyses and summaries from assessment of endpoints described in the protocol (for example, described in KGAB Protocol Table 1) are planned to be included in a clinical study report (CSR). Analyses and summaries for key safety data are also planned to be included in the CSR. Results from additional efficacy analysis and other safety analyses may also be provided in the CSR as deemed appropriate.

Any change to the data analysis methods described in the protocol will require a protocol amendment ONLY if it changes a principal feature of the protocol. Any other change to the data analysis methods described in the protocol and the justification for making the change will be described in the CSR.

All statistical processing will be performed using SAS® unless otherwise stated. Some of the analyses described in this document will be incorporated into interactive display tools instead of or in addition to static displays. Except where noted, all statistical tests will be two-sided and will be performed at the 0.05 level of significance.

The Schedule of Visits and Procedures outlined in the protocol specifies the allowable windows for assessments. Assessments performed outside these windows will not be excluded from any analysis, unless specified otherwise.

6.1.1. Analysis Populations

Analysis populations are defined in [Table KGAB.6.1](#) along with the analysis they will be used to conduct. [Table KGAB.6.2](#) describes the treatment groups and the comparisons for each study period and the analysis population.

[Figure KGAB.6.1](#) shows a pictorial description of all the analysis populations.

[figure not shown]

Figure KGAB.6.1. Study periods and analysis populations.

Table KGAB.6.1. Analysis Populations

Population	Description
All Entered Patients	All patients who signed informed consent. Patient flow will be summarized.
Intent-to-Treat (ITT) Population	All randomized patients, even if the patient does not take the assigned treatment, does not receive the correct treatment, or otherwise does not follow the protocol. Patients will be analyzed according to the treatment to which they were assigned. Unless otherwise specified, efficacy and health outcomes analyses for the Induction period will be conducted on this population.
Safety Population	All randomized patients who received at least 1 dose of study treatment during Induction Period. Safety analyses for Induction period will be conducted on this population.
Maintenance Primary Population (MPP)	All patients who were randomized to Lebrikizumab 250 mg Q2W at Baseline Visit and re-randomized to Lebrikizumab 250 mg Q2W, Lebrikizumab 250 mg Q4W or placebo at Week 16 and received at least 1 dose of study treatment during the maintenance period. Patients will be analyzed according to the treatment to which they were re-randomized. Only information prior to escape will be presented. Efficacy, health outcomes, and safety analyses for the maintenance period will be conducted on the Maintenance Primary population
Maintenance Secondary Population (MSP)	Including patients who were randomized to placebo at Baseline Visit and re-randomized to Lebrikizumab 250 mg Q2W, Lebrikizumab 250 mg Q4W or placebo at Week 16, and received at least one dose of study treatment during the maintenance period. Selective efficacy analyses for the maintenance period will be conducted on the Maintenance Secondary Population. Patients will be analyzed according to the treatment to which they were re-randomized. Only information prior to escape will be presented.
Maintenance W16 Escape Population	Including patients who were NOT re-randomized to Lebrikizumab 250 mg Q2W, Lebrikizumab 250 mg Q4W or placebo but assigned to escape arm at Week 16, and received at least one dose of study treatment during the maintenance period. Selective efficacy analyses for the maintenance period will be conducted on the Maintenance W16 Escape Population.
Maintenance W24-48 Escape Population	Including patients from Maintenance Primary and Secondary Population who escaped to Lebrikizumab 250 mg Q2W due to EASI-50 non-response at Week 24, 32, 40 or 48. Selective efficacy analyses for the maintenance period will be conducted on the Maintenance W24-48 Escape Population
All Lebrikizumab Safety Population	All randomized patients who received at least 1 dose of lebrikizumab treatment during Combined Induction and Maintenance Periods. Safety analyses for the Combined Induction and Maintenance Periods will be conducted on All Lebrikizumab Safety Population. Selective safety analyses for the Combined Induction and Maintenance Periods plus the follow-up Period will be conducted on All Lebrikizumab Safety Population.

Abbreviations: EASI = Eczema Area and Severity Index; IGA = Investigator Global Assessment;

Table KGAB.6.2. Treatment Groups and Comparisons for Each Study Period and Analysis Population

Study Period	Analysis Population	Treatment Groups	Abbreviation	Inferential Comparisons When Applicable
Induction Period	ITT; Safety	Placebo; Lebrikizumab 250 mg Q2W	PBO; LEB250Q2W	LEB250Q2W vs PBO
Maintenance Blinded Period	Maintenance Primary Population	Lebrikizumab_Res/Placebo; Lebrikizumab_Res/Lebrikizumab 250 mg Q4W; Lebrikizumab_Res/Lebrikizumab 250 mg Q2W; Total Lebrikizumab_Res/ Lebrikizumab (Safety analysis only)	LEB_Res/PBO; LEB_Res/LEB250Q4W; LEB_Res/LEB250Q2W; Total LEB_Res/LEB (Safety analysis only)	LEB_Res/LEB250Q4W vs LEB_Res/PBO; LEB_Res/LEB250Q2W vs LEB_Res/PBO
Maintenance Blinded Period	Maintenance Secondary Population	Placebo_Res/Placebo; Placebo_Res/Lebrikizumab 250 mg Q4W; Placebo_Res/Lebrikizumab 250 mg Q2W	PBO_Res/PBO; PBO_Res/LEB250Q4W; PBO_Res/LEB250Q2W	No Between-Group or Overall Comparisons
Maintenance Escape Period	Maintenance W16 Escape Population	Lebrikizumab_NonResp/ Lebrikizumab 250 mg Q2W; Placebo_NonResp/Lebrikizumab 250 Q2W	LEB_NonResp/ LEB250Q2W; PBO_NonResp/ LEB250Q2W	No Between-Group or Overall Comparisons
Maintenance Escape Period	Maintenance W24-48 Escape Population	Lebrikizumab 250 mg Q2W/Placebo/ Lebrikizumab 250 mg Q2W; Lebrikizumab 250 mg Q2W/Lebrikizumab 250 mg Q4W/Lebrikizumab 250 mg Q2W; Lebrikizumab 250 mg Q2W/Lebrikizumab 250 mg Q2W/Lebrikizumab 250 mg Q2W; Placebo/Placebo/Lebrikizumab 250 mg Q2W; Placebo/Lebrikizumab 250 mg Q4W/Lebrikizumab 250 mg Q2W; Placebo/Lebrikizumab 250 mg Q2W/Lebrikizumab 250 mg Q2W	LEB250Q2W/PBO/LEB250Q2W ; LEB250Q2W/ LEB250Q4W/ LEB250Q2W; LEB250Q2W/ LEB250Q2W/ LEB250Q2W; PBO/PBO/LEB250Q2W; PBO/LEB250Q4W/LEB250Q2W ; PBO/LEB250Q2W/LEB250Q2W	No Between-Group or Overall Comparisons

Treatment Groups and Comparisons for Each Study Period and Analysis Population

Study Period	Analysis Population	Treatment Groups	Abbreviation	Inferential Comparisons When Applicable
Combined Induction and Maintenance Periods	All Lebrikizumab Safety Population	Any Lebrikizumab	N/A	No Between-Group or Overall Comparisons
Combined Induction and Maintenance Periods + FU	All Lebrikizumab Safety Population	Any Lebrikizumab	N/A	No Between-Group or Overall Comparisons

Abbreviations: FU = follow-up; ITT = intent-to-treat; LEB = lebrikizumab; NonResp = non-responder; PBO = placebo; Q2W = every 2 weeks; Q4W = every 4 weeks; Res = responder.

6.1.2. General Considerations for Analyses During Induction Period

Induction Period starts after the first injection of study treatment at Baseline Visit (Day 1) and ends prior to the first injection of study treatment at Week 16 or the early termination visit (ETV) (between Day 1 and Week 16). For patients who are randomized but not dosed, the Induction Period starts on the date of randomization.

Baseline will be defined as the last available value before the first injection for efficacy and health outcome analyses. In most cases, this will be the measure recorded at Baseline Visit (Day 1). If the patient does not take any injection, the last available value on or prior to randomization date will be used. Change from baseline will be calculated as the visit value of interest minus the baseline value.

For Pruritus Numeric Rating Scale (NRS) and Sleep-Loss due to Pruritus collected via eDiary, the baseline period is the 7-day window prior to the first injection. A patient must have responses on at least 4 of 7 days to calculate a baseline weekly mean. If a patient has 3 or fewer responses, the baseline mean value will be considered missing. eDiary data for Pruritus NRS and Sleep-loss due to Pruritus are mapped to study visit per [Appendix 1](#).

For the safety analyses, the following baselines will be used. For safety analyses using a baseline period, the baseline period is defined as the time from Screening Visit to the date/time of the first injection in Induction Period.

- Treatment-emergent adverse events (TEAEs): baseline will be all results recorded during the baseline period.
- Treatment-emergent abnormal laboratory and vital signs results: baseline will be all results recorded during the baseline period.
- Change from baseline to last post-baseline observation or to each scheduled post baseline visit for laboratory and vital signs results: baseline will be the last scheduled non-missing assessment recorded during the baseline period.

The randomization to treatment groups is stratified by geographical region (US versus EU versus rest of world), age (adolescent patients 12 to <18 years versus adults ≥ 18 years) and baseline disease severity (IGA 3 versus 4) as described in Section 5.3. The countries will be categorized into geographic regions for analysis (Section 6.3). Unless otherwise specified, the statistical analysis models for Induction Period will adjust for geographic region, age and baseline disease severity.

For assessments of the primary endpoints and other binary efficacy and health outcomes endpoints, the following will be provided:

- Crude proportions for each treatment group along with the 95% two-sided asymptotic (that is, not continuity corrected) confidence intervals (CIs) will be provided.

- The estimated common risk difference along with 95% CIs. The common risk difference is the difference in proportions adjusted for the stratification factors as mentioned in Section 6.3. SAS® PROC FREQ will be used for the estimates and CIs, where the CIs are calculated by using Mantel-Haenszel-Sato method (Sato 1989).
- Cochran-Mantel-Haenszel (CMH) test will be used to compare the treatment groups while adjusting for the stratification factors. The CMH p-value will be reported, and the CMH adjusted odds ratio along with the 95% two-sided asymptotic (that is, not continuity corrected) CIs.

Treatment comparisons of key continuous efficacy variables and health outcome variables at each postbaseline time point will be made using analysis of covariance (ANCOVA) with the following in the model: treatment group, baseline value, and stratification factors mentioned in Section 6.3. Type III tests for least squares (LS) means will be used for statistical comparison between treatment groups. The LS mean difference, standard error, p-value, and 95% CI, unless otherwise specified, will also be reported.

Treatment comparisons of other continuous efficacy variables and health outcome variables with multiple postbaseline measurements will be made using mixed-model for repeated measures (MMRM). When MMRM is used, the model includes treatment, baseline value, visit, the interaction of the baseline value-by-visit, the interaction of treatment-by-visit, and the stratification factors mentioned in Section 6.3 as fixed factors. The covariance structure to model the within-patient errors will be unstructured. If the unstructured covariance matrix results in a lack of convergence, the heterogeneous Toeplitz covariance structure, followed by the heterogeneous autoregressive covariance structure will be used. The restricted maximum likelihood (REML) will be used. The Kenward-Roger method will be used to estimate the denominator degrees of freedom. Type III tests for the LS means will be used for the statistical comparison; the 95% CI will also be reported.

For variables that are not collected at each postbaseline visit, data may exist at visits where the variable was not scheduled to be collected. In these situations, data from the early discontinuation visit that do not correspond to the planned collection schedule will be excluded from the MMRM analysis (Andersen and Millen 2013). Also for by-visit summaries/displays such as boxplots, the weeks when data was not scheduled to be collected may not be displayed. However, unscheduled assessments within any defined study period will still be used in the shift analyses, and for imputing values for the change from baseline to last observation carried forward (LOCF) endpoint analyses.

The Kaplan-Meier (KM) product limit method maybe used to estimate the survival for time to event analyses. The log-rank test stratified by the stratification factors mentioned in Section 6.3 will be reported. A Kaplan-Meier plot of the time to event by treatment group may be provided.

Unless specified otherwise, Fisher's exact test will be used for adverse events (AEs) and other categorical safety measures. Odds ratios will be created with lebrikizumab treatment as the numerator, and placebo as the denominator. Continuous vital sign and laboratory values will be analyzed by an ANCOVA with treatment and baseline value in the model.

6.1.3. General Considerations for Analyses During Maintenance Period

Maintenance Period starts at the first injection of study treatment at Week 16 and ends on the date of Week 52 or the ETV (between Weeks 16 and 52) unless specified otherwise.

For the efficacy and health outcome analyses, baseline is defined as the last available value before the first injection in Induction Period and, in most cases, will be the value recorded at Baseline Visit (Day 1).

Unless otherwise specified, efficacy and health outcome scores at Week 16 prior to entering Maintenance Period will be presented for the visitwise reports for Maintenance Period.

Unless specified otherwise, for the safety analyses during Maintenance Period, baseline is defined as the last available value before first injection in Maintenance Period. In most cases, this will be the measure recorded at Week 16. For TEAEs, baseline is the events ongoing just prior to the first injection of the study drug injection at Week 16.

For patients in the Maintenance Primary and Secondary Population who met escape criteria (EASI-50 nonresponse) and escaped to lebrikizumab 250 mg Q2W at Weeks 24, 32, 40 and 48, only data in the Maintenance blinded period (up to the time of escape) will be included in both efficacy and safety analyses.

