6.1.3.1. Maintenance Primary Population

Unless otherwise specified, treatment comparisons of categorical efficacy and health outcomes variables will be analyzed using CMH test with treatment group and covariates as mentioned in Section 6.3 in the model. The CMH p-value will be reported, and the CMH adjusted odds ratio along with the 95% two-sided asymptotic (that is, not continuity corrected) CIs.

Each continuous efficacy and health outcomes measure score, change from baseline and percent improvement from baseline will be summarized by treatment group at all scheduled visits during Maintenance Period including Week 52, using descriptive statistics (n, mean, standard deviation (SD), median, minimum, and maximum).

Treatment comparisons for continuous efficacy and health outcome variables will be made using ANCOVA model as specified.

When the ANCOVA is used, the model will include treatment, baseline value and covariates as mentioned in Section 6.3. The ANCOVA analysis will be conducted as described in Section 6.1.2.

The KM product limit method will be used to estimate the survival for time to event analyses (e.g., time to loss of IGA response or time to loss of EASI-50 or time to loss of EASI-75). The stratified log-rank test will be performed with treatment group and covariates as mentioned in Section 6.3 in the model. A KM plot of the time to event by treatment group may be provided.

Unless specified otherwise, Fisher's exact test will be used for AEs and other categorical safety measures. Odds ratios will be created with lebrikizumab treatment as the numerator and placebo

as the denominator. Continuous vital sign and laboratory values will be analyzed by an ANCOVA model with treatment and baseline value as independent variables.

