6.14.1. Extent of Exposure

Duration of exposure to study treatment will be summarized by treatment group. Drug interruption time period due to the use of systemic rescue therapies will not be removed from study drug exposure calculations as described in compound level safety standards.

The duration of exposure will be calculated as:

$$\begin{aligned} & \textit{Duration of exposure (days)} \\ & = \textit{Date of last visit (scheduled or unscheduled) in the specified Treatment Period} \\ & \quad - \textit{Date of first dose in Treatment Period} + 1 \end{aligned}$$

The number and percentage of patients in each of the following categories will be included in the summaries:

- >0, ≥7, ≥14, ≥30, ≥60, ≥90, ≥112, ≥120 days for Induction Period (for Maintenance Period, use ≥30, ≥60, ≥90, ≥120, ≥150, ≥180, ≥210, ≥240, and ≥252 days). Note that patients may be included in more than 1 category.
- >0 to <7, ≥7 to <14, ≥14 to <30, ≥30 to <60, ≥60 to <90, ≥90 to <120, ≥120 days (for Maintenance Period, use >0 to <30, ≥30 to <60, ≥60 to <90, ≥90 to <120, ≥120 to <150, ≥150 to <180, ≥180 to <210, ≥210 to <240, ≥240 to <252, ≥252).

Additional exposure ranges may be considered if necessary. No p-values will be reported.

The summaries will also include the following information:

- Total exposure in patient years, calculated as:

Total exposure in patient years

$$= \frac{\text{Sum of duration of exposures for all patients in treatment group}}{365.25}$$

- Mean and median total dose. Total dose (in mg) is calculated by the number of active injections taken during the treatment period multiplied by dose. For patients in Safety Population randomized to lebrizumab 250 mg Q2W or patients in Maintenance Primary Population re-randomized to lebrizumab 250 mg Q2W or Q4W, the total dose (in mg) taken during Induction Period or Maintenance Period will be calculated as follows: *Total lebrizumab dose = Total number of active injections (including loading doses, if any) received in Induction Period or Maintenance Period × 250.*
- Total number of injections received will be derived based on the *Study Drug Administration* eCRF page and the response to the question “Did you or a caregiver successfully inject the study drug?” on the Dosing Diary eCRF page.

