6.14.2. Adverse Events

A TEAE is defined as an event that first occurred or worsened in severity after baseline. The MedDRA Lowest Level Term (LLT) will be used in the treatment-emergent computation. The maximum severity for each LLT during the baseline period will be used as baseline. The treatment period will be included as postbaseline for the analysis. For events with a missing severity during the baseline period, it will be treated as ‘mild’ in severity for determining treatment-emergence. Events with a missing severity during the postbaseline period will be treated as ‘severe’ and treatment-emergence will be determined by comparing to baseline severity. For events occurring on the day of first taking study medication, it will be assumed to be posttreatment.

The planned summaries for adverse events are provided in [Table KGAB.6.13](#), and are described more fully in compound level safety standards and in the adverse event-related PhUSE white paper [Analysis and Displays Associated with Adverse Events: Focus on Adverse Events in Phase 2-4 Clinical Trials and Integrated Summary Document (PhUSE 2017)].

Summary tables as described in [Table KGAB.6.13](#) will be presented for the following periods/analysis populations as indicated. Summary tables will include the number and percentage of patients reporting an event. For events that are gender-specific (as defined by MedDRA), the number of participants at risk will include only patients from the given gender.

- Induction Period (Safety Population, S)
- Maintenance Blinded Period (Maintenance Primary Population, M)
- Combined Induction Period and Maintenance Period, Combined Induction and Maintenance Periods Plus Follow-Up Period [selective analysis] (All Lebrizumab Safety Population, A)

Table KGAB.6.13. Summary Tables/Listing Related to Adverse Events

Analysis	Population (Section 6.1.1)
Overview of AEs	S, M, A
Summary of TEAE by PTs	S, M
Summary of TEAE by PTs occurring in $\geq 1\%$ of patients	S, M
Summary of TEAE by PTs within SOC	S, M, A
Summary of TEAE PTs by maximum severity	S, M
Summary of SAE by PT within SOC	S, M, A
Summary of AEs leading to treatment discontinuation by PT with SOC	S, M, A
Summary of TEAE possibly related to study drug by PTs within SOC	S, M
Listing of SAEs (including Death)	ITT
Listing of primary AEs leading to study treatment discontinuation	ITT
Listing of TEAE (for Japan submission only)	S

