Abbreviations: A = All Lebrizumab Safety Population; AE = adverse event; ITT = Intent-to-Treat; M = Maintenance Primary Population; PT = Preferred Term; SAE = serious adverse event; S = Safety Population; SOC = System Organ Class; TEAE = treatment-emergent adverse event.

Statistical comparisons will be performed for Safety Population and Maintenance Primary Population using Fisher's exact test. Odds ratio will be provided.

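### Maintenance adverse events are compared as crude percentages although analysed follow-up ends at escape and may differ by arm; time at risk should be added

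*SAP*

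**What the plan says.** SAP 5.1.3.2 sends to the open-label Escape Arm "those patients not maintaining an EASI-50 response following re-randomization at Week 24, 32, 40, or 48". Section 6.1.1 limits the Maintenance Primary Population accordingly: "Only information prior to escape will be presented". Section 6.1.3 repeats the limit and names safety explicitly: "only data in the Maintenance blinded period (up to the time of escape) will be included in both efficacy and safety analyses".

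For AEs, section 6.14.2 specifies that "Summary tables will include the number and percentage of patients reporting an event", and then that "Statistical comparisons will be performed for Safety Population and Maintenance Primary Population using Fisher's exact test", with odds ratios. Section 6.1.3.1 gives the same default. Table KGAB.6.2 sets the comparisons as Q2W versus placebo and Q4W versus placebo.

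Section 6.14.1 does define a follow-up total ("Total exposure in patient years, calculated as"), and section 6.7 reports how many patients entered escape. Neither quantity enters any AE analysis specified in the SAP or protocol.

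**The concern.** Escape is triggered by the efficacy outcome. In a randomised-withdrawal design, loss of response is expected more often on placebo, so the length of analysed follow-up depends on treatment effect. A crude percentage compared by Fisher's test has a clear reading as a risk only when the arms are followed for similar times.

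The SAP deals with this for efficacy. Transfer to escape is an intercurrent event with a stated strategy in all four maintenance estimands (6.2.2), and time to loss of response is analysed by Kaplan-Meier with censoring. The same truncation gets no treatment for safety.

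At stake is the only randomised safety comparison after Week 16 and the only one that includes Q4W. The All Lebrikizumab Safety Population has no comparator (Table KGAB.6.2). The affected tables include overall treatment-emergent AEs, serious AEs and AEs leading to treatment discontinuation (Table KGAB.6.13).

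**Working it through.** **The plan's own figures.** The documents give no escape rate, no maintenance AE rate and no calculation for this comparison, so there is nothing to reproduce here. Their sample-size inputs are used only for arm sizes in step 5.

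**Inputs from the documents.** Maintenance lasts 36 weeks. Escape is possible at Weeks 24, 32, 40 and 48, which is t = 8, 16, 24 and 32 weeks after re-randomisation.

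**Assumptions.**
- Escape is 20%, 40% or 60% on placebo, paired with 5%, 10% and 10% on lebrikizumab.
- Timing is either even over the four visits (mean 20 weeks) or early, with 70% of escapes at Week 24 and 10% at each later visit (mean 0.7×8 + 0.1×(16+24+32) = 12.8 weeks).
- The true hazard is constant and identical in all arms, and there is no other dropout.

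**Step 1. Formulas.** For a true 36-week risk R, the weekly hazard is h = −ln(1−R)/36 and F(t) = 1 − exp(−ht). With escape proportion e, the observed percentage is (1−e)·R + e·(weighted mean of F at the escape times). Mean observation is (1−e)·36 + e·(mean escape time).

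**Step 2. Worked case: R = 20%, even timing, escape 40% versus 10%.**
- h = −ln(0.80)/36 = 0.006198 per week. F(8), F(16), F(24), F(32) = 4.84%, 9.44%, 13.82%, 17.99%; mean 11.52%.
- Placebo: 0.6×20% + 0.4×11.52% = 16.6%; observation 0.6×36 + 0.4×20 = 29.6 weeks.
- Lebrikizumab: 0.9×20% + 0.1×11.52% = 19.2%; observation 0.9×36 + 0.1×20 = 34.4 weeks.
- Risk ratio 1.15 and odds ratio 1.19, where the true value of both is 1.
- Expected time at risk to first event is observed risk divided by h: 26.8 weeks on placebo and 30.9 on lebrikizumab. Events divided by time at risk therefore returns the same rate in both arms, a ratio of 1.00.

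**Step 3. Range of spurious risk ratios (lebrikizumab / placebo).**

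| Escape, placebo / leb | Timing | Mean weeks, placebo / leb | R = 5% | R = 20% | R = 50% |
|---|---|---|---|---|---|
| 20% / 5% | even | 32.8 / 35.2 | 1.07 | 1.07 | 1.06 |
| 40% / 10% | even | 29.6 / 34.4 | 1.16 | 1.15 | 1.13 |
| 60% / 10% | even | 26.4 / 34.4 | 1.30 | 1.28 | 1.25 |
| 20% / 5% | early | 31.4 / 34.8 | 1.11 | 1.11 | 1.10 |
| 40% / 10% | early | 26.7 / 33.7 | 1.26 | 1.25 | 1.23 |
| 60% / 10% | early | 22.1 / 33.7 | 1.52 | 1.50 | 1.45 |

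Odds ratios are further from 1 for common events: at R = 50% with even timing they are 1.12, 1.26 and 1.48. Equal escape in the two arms (40% each) gives exactly 1.00.

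**Step 4. Where the direction changes.**
- Events in the first 8 weeks precede any possible escape, so escape causes no bias.
- For an event with no placebo incidence, placebo stays at 0 while a true 10.0% on lebrikizumab (10% escape, even timing) is seen as 9.6%. Lebrikizumab looks marginally safer.
- For a drug-caused event (20% on lebrikizumab) with an assumed 8 weeks of residual effect after withdrawal and escape 40% versus 10%, the full-follow-up risk ratio is 4.13 and the crude ratio 3.96, an understatement. The exposure-adjusted ratio is 3.63 against a full-follow-up rate ratio of 4.41.

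**Step 5. Effect on Fisher's test.** Lebrikizumab patients: 400×2/3 = 267. At the 48.0% EASI-75 rate used for sample size, about 128 are re-randomised; 2:2:1 gives about 51:51:26. By exact enumeration for 51 versus 26 with even timing, two-sided rejection for a 50% event is 3.2% with no escape, 4.9% at 40%/10% escape and 8.5% at 60%/10%. For a 20% event it moves from 3.4% to 3.6% at 40%/10%.

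**The case against.** A reader might infer that lebrikizumab will simply look less safe than it is. The documents do not support that as a general statement. They give no escape rates, and the direction requires more escape on placebo together with a similar, roughly constant hazard. Step 4 shows cases with no bias and with reversal. The Phase 2b conjunctivitis pattern (2.6% versus 0, Protocol 1.3.1.3) resembles the zero-placebo case.

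A reader might also infer that AEs go unobserved after escape. They do not. AE collection continues in the Escape Arm (Protocol Appendix 1, Table 7), and these events enter the All Lebrikizumab Safety Population. Only the between-arm comparison is truncated, with good reason: it keeps AEs on open-label lebrikizumab out of the placebo column.

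Other points stand as limits:
- SAP 6.14 restricts safety p-values to flagging and warns against over-reading them. That caveat does not cover the percentages and odds ratios.
- Special safety topics, including AEs of special interest, are by default not summarised for this population (6.14.6).
- Exposure by arm and escape counts are reported separately, so an attentive reader could see unequal follow-up.
- Section 6.14.2 refers to compound-level safety standards that are not among the documents. Time-at-risk analyses may be specified there.
- Escape reflects disease activity, so censoring at escape may be informative. In the residual-effect case the exposure-adjusted ratio missed its full-follow-up target by more than the crude ratio missed its own. This argues against replacing the crude table, but not against adding rates beside it.

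**Conclusion.** The concern holds in a conditional form. The SAP text ties analysed safety follow-up to an efficacy-driven exit and then compares crude percentages with no time at risk. If placebo patients escape more often, the comparison is distorted against lebrikizumab for AEs with a similar, constant hazard in all arms. The spurious risk ratio is about 1.06–1.30 with even escape timing, and up to about 1.5 if 70% of escapes fall at Week 24. The escape rates and timing behind these figures are assumed. The harm is mainly to the percentages and odds ratios: inflation of Fisher false flags is modest, and exceeds 5% in the cases computed only for a 50% event at 60% versus 10% escape. Because direction depends on the type of AE, the crude table cannot be interpreted without time at risk. This is a worthwhile, inexpensive improvement; it does not invalidate the safety evaluation.

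**What to change.** In SAP 6.14.2, for the Maintenance Primary Population:

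- Beside n (%), add the number of patients with a first event per 100 patient-years at risk, with time ending at first event, escape, discontinuation or Week 52. Give rate differences and 95% CIs for each lebrikizumab arm against placebo.
- Show mean observation time per arm in the AE tables.
- Add a cumulative-incidence display, or the proportion of patients with an AE by Week 24, before escape can truncate follow-up.
- Keep the Fisher p-values and odds ratios, labelled as unadjusted for unequal follow-up.

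If the compound-level standards already specify such rates for this population, a cross-reference would cover that part.

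The cost is SAP wording and a small amount of programming. The patient-years in 6.14.1 run to the last visit in the period, so time to first event must be derived for each term. The rates assume a roughly constant hazard and non-informative censoring at escape; they should supplement the crude table, not replace it.
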